4.5 Adjustment for Covariates

No formal model-based inferential analyses are planned using covariates and interactions.

4.6 Subgroup Analysis

To evaluate the consistency of immunogenicity results and safety profiles across subgroups, immunogenicity outcome (TNA NF₅₀ on Day 29 and Day 64) and safety endpoints (incidences of TEAEs, SAEs, and e-diary reactogenicity) will be summarized for AV7909 (three lots pooled) and BioThrax groups by age (18-30, 31-50 and 51-65), sex (Male, Female), and race (Caucasian, African American, Other/More than One Race). No formal statistical hypothesis testing will be performed.

4.7 Multicenter Study

This study is expected to enroll 3850 participants at approximately 30-40 sites in the United States. Because of the large number of sites participating, test statistics adjusted for site are not planned. Subject enrollment and protocol deviations will be summarized by site.

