2.5 Randomization and Blinding

2.5.1 Randomization

At the Day 1 (randomization) visit, after the PI has confirmed that the participant meets all of the inclusion criteria and none of the exclusion criteria, the participant will be randomly assigned to one of the four study groups with the ratio of 2:2:2:1 (block size of 7) via an interactive voice and/or web response system (IxRS). Randomization will be stratified by site. Racial distribution will be monitored among recruited participants. Participants who are randomized and do not receive vaccination on the same day will be withdrawn from the study. Randomized participants who withdraw from the study for any reason will not be replaced in this trial.

A randomization plan describing the method of treatment allocation and implementation of this method will be prepared and finalized prior to randomization of the first participant.

A screen failure is a participant from whom informed consent is obtained and documented in writing, but who is not subsequently randomized to study treatment. Participants who are screen failures are permitted to be rescreened one time (only) according to the PI's discretion. If a participant is rescreened, a new subject ID will be assigned. To link records to the same participant, the participant's previous subject ID will be recorded in the eCRF along with the new subject ID. Participants who complete the rescreening and are randomized in the study will not be considered screen failures.

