6.2 Primary Immunogenicity Endpoints

6.2.1 AV7909 Lot Consistency

6.2.1.1 Lot Consistency Based on GMT Ratio of TNA NF₅₀ at Day 64

The AV7909 lot consistency analysis is performed by pair-wise comparison of the two-sided 95% CI on GMT ratio for TNA NF₅₀ in each pair of lots (Lot 1 vs. Lot 2, Lot 2 vs. Lot 3, and Lot 1 vs. Lot 3) on Day 64. The lot consistency endpoint based on the GMT ratio for TNA NF₅₀ will be met if all three 95% CIs fall within the equivalence range of [0.5, 2.0]. The linear regression model will be fitted with log₁₀ NF₅₀ (Day 64) as the dependent variable and lot as the independent variable (categorical), assuming common residual variance. The mean differences in log₁₀ NF₅₀ between all pairs of lots will be calculated with 95% CIs. These will be transformed (anti-log) back to the scale of GMT ratios.

6.2.1.2 Lot Consistency Based on Protective Level of Immunogenicity at Day 64

The protective level of immunogenicity in each of the three AV7909 lots at Day 64, under the US FDA's Animal Rule, is assessed by the proportion of participants with TNA NF₅₀ values ≥ 0.56 on Day 64. The proportion and two-sided 95% CI (exact Clopper-Pearson confidence limits) for the proportion will be provided for each of the three AV7909 lots. This lot consistency based on the protective level of immunogenicity will be met if the LB of the two-sided 95% CI of the proportion is $\geq 40\%$ for all three AV7909 lots.

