6.2.2 AV7909 Immunogenicity

6.2.2.1 AV7909 Immunogenicity at Day 64

The immunogenicity of AV7909 on Day 64 will be assessed by the proportion of participants pooled across all three AV7909 lots with TNA NF₅₀ values ≥ 0.56 on Day 64. The proportion and two-sided 95% CI (exact Clopper-Pearson confidence limits) for the proportion will be provided for the combined AV7909 group (three lots pooled). AV7909 will be considered as achieving a protective level of immunogenicity at Day 64 if the LB of the two-sided 95% CI of the proportion is $\geq 40\%$.

6.2.2.2 AV7909 Immunogenicity Based on Non-inferiority vs BioThrax at Day 64

Non-inferiority of AV7909 versus BioThrax on Day 64 is satisfied if the LB for the two-sided 95% lower CI of the difference (AV7909 - BioThrax) in the proportion of participants with TNA NF₅₀ values ≥ 0.29 in the combined AV7909 group (three lots pooled) versus BioThrax group is $> -15\%$.

The within-group proportions and the associated two-sided 95% CIs (exact Clopper-Pearson confidence limits) will be provided for the combined AV7909 group (three lots pooled) and

BioThrax group. The treatment difference in proportion between the combined AV7909 group and BioThrax group and two-sided 95% lower CI will be calculated using Newcombe score method.

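### Randomisation is stratified by site, but the lot-ratio and non-inferiority analyses ignore site; if titres differ between sites, the lot-ratio intervals are slightly conservative.

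*SAP*

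**What the plan says.** SAP 2.5.1 allocates participants 2:2:2:1 in blocks of 7 and states: "Randomization will be stratified by site". Protocol 4.1 says the same, and no other stratification factor is named.

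The analysis sections do not use site:

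- SAP 4.7 expects "approximately 30-40 sites in the United States" and gives the number of sites as its only reason for not adjusting: "Because of the large number of sites participating, test statistics adjusted for site are not planned".
- SAP 4.5 adds: "No formal model-based inferential analyses are planned using covariates and interactions".
- SAP 6.2.1.1 (endpoint 1a) regresses Day 64 log10 NF50 with "lot as the independent variable (categorical), assuming common residual variance". All three pairwise 95% intervals must lie within 0.5 to 2.0.
- SAP 6.2.2.2 (endpoint 2b) says of the difference in proportions that the "two-sided 95% lower CI will be calculated using Newcombe score method". No stratification is mentioned.
- SAP 6.2.1.2 and 6.2.2.1 (endpoints 1b and 2a) use exact Clopper-Pearson limits for single-group proportions.

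Site appears in the summaries of enrolment and protocol deviations (SAP 4.7, 5.1 and 5.2). No site-adjusted sensitivity analysis of titres is planned.

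**The concern.** Blocking within site balances the lots across sites, so differences between sites largely cancel from the true variance of a lot comparison. A model with lot alone does not recognise this. It puts between-site variation into the residual and reports a standard error larger than the one the design delivers. The usual practice is to include the stratification factor in the analysis.

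The reason given in SAP 4.7 would matter if sites were tiny or the model could not carry the terms. With the planned Per Protocol numbers, neither applies to the lot model. What is at stake is precision in endpoint 1a, which is first in the hierarchy of SAP 4.8 and must succeed on all three pairs before any later immunogenicity test is made.

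**Working it through.** **Inputs from SAP 2.4, 4.7 and 6.2.1.1.** 800 Per Protocol participants per AV7909 lot (2400 in all) and 400 on BioThrax; coefficient of variation 100%; largest planned lot ratio 1.5; a lot ratio as low as 0.6 also mentioned; bounds 0.5 and 2.0; two-sided 95% intervals; 30 to 40 sites.

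**Assumed input.** The share of log-titre variance explained by site, written r. The documents give no value, so a range is shown.

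**1. The plan's own figure.**
- SD on the natural-log scale = sqrt(ln(1 + 1²)) = sqrt(ln 2) = 0.8326.
- SE of a lot difference = 0.8326 × sqrt(2/800) = 0.0416.
- Power at ratio 1.5 = Φ(ln(2/1.5)/0.0416 − 1.96), which exceeds 99.99%.
- At ratio 0.6 the same formula with ln(0.6/0.5) gives 99.2% for one pair.

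The stated power of more than 99% at ratio 1.5 is reproduced.

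**2. Can the model carry site?** 2400/40 = 60 and 2400/30 = 80 AV7909 participants per site, or 20 to 27 per lot per site. Adding 29 to 39 site terms to about 2400 observations costs almost nothing in degrees of freedom. For 2b there are 400/40 = 10 to 400/30 ≈ 13 BioThrax participants per site.

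**3. Effect on the 1a interval.** With site in the model the residual SD is 0.8326 × sqrt(1 − r). The unadjusted SE is therefore too large by the factor 1/sqrt(1 − r), and the actual coverage of the nominal 95% interval is 2Φ(1.96/sqrt(1 − r)) − 1. The interval factor is exp(1.96 × SE), applied by multiplying and dividing.

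| r | SE too large by | Actual coverage | Interval factor, lot only | Interval factor, with site |
|---|---|---|---|---|
| 0 | 0% | 95.0% | 1.085 | 1.085 |
| 2% | 1.0% | 95.2% | 1.085 | 1.084 |
| 5% | 2.6% | 95.6% | 1.085 | 1.083 |
| 10% | 5.4% | 96.1% | 1.085 | 1.080 |

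The largest observed ratio that still passes is 2/1.085 = 1.843 unadjusted. With site in the model at r = 10% it is 1.851.

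**4. Power, like for like.** Both analyses must be judged under the same truth. The true sampling SD of each lot mean is 0.8326 × sqrt((1 − r)/800) in both, and only the SE used in the interval differs. Simulated joint power for all three pairs, with two lots equal and the third at a ratio of 0.6 to each:

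| r | Lot only | Lot plus site | Gain |
|---|---|---|---|
| 2% | 98.6% | 98.7% | about 0.1 points |
| 5% | 98.8% | 98.9% | about 0.2 points before rounding |
| 10% | 99.0% | 99.2% | about 0.3 points before rounding |

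At the planned ratio of 1.5, power exceeds 99.99% either way.

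**5. Endpoint 2b.** Simulation with 40 unequal sites, rates of 83% and 93%, and an assumed between-site SD of 0.3 to 0.8 on the logit scale gave a site-stratified SE 0.3% to 2.5% smaller. Power was essentially unchanged.

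**The case against.** The strongest reply is that nothing here is invalid. The choice is pre-specified and openly stated, the protocol promises no site-adjusted analysis, and the error is on the cautious side. Endpoint 1a also has ample room: the interval factor is about 1.085 against bounds of 0.5 and 2.0. Titres are standardised to a common reference serum, which may limit site effects. All of this stands, and it is why the point is minor.

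Four stronger readings are tempting, and the documents do not support them.

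- **That the lot-ratio intervals are wider as a matter of fact.** This needs between-site variance in titre, and neither document gives any.
- **That every primary test is affected in this way.** Endpoints 1b and 2a are single-group proportions, where no site variation cancels between groups. The argument covers 1a and, more weakly, 2b.
- **That power at a ratio of 0.6 rises from 98.5% to as much as 99.2%.** The 98.5% assumes no site effect and the 99.2% assumes that site explains 10%. These are different truths. Under stratified randomisation the unadjusted test gains from the balance as well.
- **That adjustment would repair the effects of the assumed 25% Per Protocol exclusions.** A site term corrects a difference in site mix between lots. It does not correct selection within sites, or the Day 29 exclusion that applies to BioThrax alone.

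The reply does not rescue the rationale in SAP 4.7, which fails for the lot model. It does carry weight for 2b. At an assumed 93% response, 10 BioThrax participants at a site yield an expected 0.7 non-responders, so replacing the primary interval there is not warranted.

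**Conclusion.** The mismatch between design and analysis is real, and its stated justification does not hold for endpoint 1a. The consequence is conditional and small. The 1a standard error is about 1% to 5.4% too large if site explains 2% to 10% of log-titre variance, and correct if site explains nothing. Type I error is not inflated. The like-for-like power gain is about 0.1 to 0.3 points at a lot ratio of 0.6 and nil at 1.5. With r up to 10%, the 1a decision could change only if the largest observed ratio fell at about 1.84 to 1.85, or the smallest at the reciprocals.

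These figures rest on the plan's coefficient of variation of 100%, 800 per lot, near-balance of lots within sites, and the assumed range for r. The point is a free improvement of minor weight. It does not question the sample size or the control of error.

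**What to change.** - **SAP 6.2.1.1:** add site as a fixed effect to the lot model and take the three lot differences from it. State a rule for pooling very small sites, fixed before unblinding.
- **SAP 6.2.2.2:** keep the Newcombe interval as primary. Add a site-stratified risk difference with Mantel-Haenszel weights as a pre-specified sensitivity analysis.
- **SAP 4.5 and 4.7:** amend both so that they allow the site term in 1a and the sensitivity analysis in 2b, and no longer cite the number of sites as the reason for not adjusting the lot model. The statement of no site adjustment can remain for 1b, 2a and the Day 29 endpoint.

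The cost is SAP wording, one additional factor in one model, one supplementary analysis and the pooling rule. No change to sample size, data collection or trial conduct is needed.

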4.8 Multiplicity Adjustment

The primary immunogenicity endpoints will be tested in the hierarchy below. Testing of the next endpoint will only be carried out when all previous endpoints are met. According to the closed testing principle, this procedure ensures that the overall type I error rate is controlled at less than 5% and no additional adjustment is needed.

- 1a. AV7909 Lot Consistency Based on GMT ratio of TNA NF₅₀ at Day 64:** the 95% CIs for the Day 64 TNA NF₅₀ geometric mean ratios between all three pairs of AV7909 groups (Lot 1 vs. Lot 2, Lot 2 vs. Lot 3, and Lot 1 vs. Lot 3) are within 0.5 and 2.0.
- 1b. AV7909 Lot Consistency Based on Protective Level of Immunogenicity at Day 64:** protective level of immunogenicity in all three consecutive AV7909 lots as demonstrated by lower bound (LB) of the two-sided 95% CI $\geq 40\%$ for the proportion of AV7909 participants in each of the three lots achieving a TNA NF₅₀ ≥ 0.56 at Day 64.

Together, the two endpoints **1a** and **1b** must both be met to demonstrate AV7909 lot consistency.

- 2a. AV7909 Immunogenicity at Day 64:** once lot consistency is demonstrated, the immunogenicity data on Day 64 will be pooled across all three AV7909 lots. AV7909 will be considered as achieving a protective level of immunity under the US FDA's Animal Rule at Day 64 if the LB for the two-sided 95% CI for the proportion of participants with TNA NF₅₀ values above the specified threshold of protection (≥ 0.56) is $\geq 40\%$.
- 2b. AV7909 Immunogenicity Based on Non-inferiority vs BioThrax at Day 64:** the difference in the proportion of participants with TNA NF₅₀ values above the specified threshold of protection (≥ 0.29) will be calculated using the pooled AV7909 groups versus the BioThrax group. Non-inferiority is demonstrated if the two-sided 95% lower CI of difference in proportions (AV7909 minus BioThrax) is above -15%.

Once all the primary endpoints (AV7909 lot consistency and immunogenicity) are satisfied, the secondary immunogenicity endpoint, AV7909 immunogenicity at Day 29, will be considered appropriately immunogenic under the US FDA's Animal Rule on Day 29 if the LB for the two-sided 95% CI for the proportion of participants pooled from all three AV7909 groups with TNA NF₅₀ values above the specified threshold of protection (≥ 0.15) is $\geq 67\%$.

4.9 Data Issues Handling

4.9.1 Oral Temperature Data Errors

Oral temperatures are reported by participants in the e-diary for post vaccination reactogenicity. The numeric temperature values and the associated toxicity grades with temperatures less than 90 °F or greater than 110 °F will be set to null in the analysis.

4.9.2 Duplicate Enrollment at Different Sites

Eight subjects have been identified as being the same subjects that enrolled in 2 different sites, meaning only 4 unique subjects should be present in the study data and report. Data handling plans with respect to SDTM and data analysis are specified in [Appendix III](#) and [Appendix IV](#).

5 STUDY POPULATION CHARACTERISTICS

5.1 Subject Disposition

Subject disposition will be summarized for all participants who sign and date the ICF. Tabulations will include the number of participants screened, randomized, vaccinated, completed study treatment (received all study vaccinations), discontinued study treatment, and withdrawn from the study prior to completion of the 12-month follow-up. Reasons for discontinuation of treatment and withdrawal from the study will be summarized.

The number and percentage of participants in each analysis population will be summarized by study group and overall for all randomized participants.

The number and percentage of participants enrolled by site will be provided by study group and overall based on the ITT population. Reasons for screen failure and reasons for exclusion from PP population will be summarized.

A listing of participants who discontinued IP or withdrawn from the study with reasons will be provided.

5.2 Protocol Deviations

Protocol deviations defined in [Section 3.1](#) will be summarized by site and deviation severity and category for each of the four study groups and overall for ITT Population.

A listing of protocol deviations will be provided.

5.3 Demographics and Baseline Characteristics

5.3.1 Subject Demographics and Baseline Characteristics

The following demographics and baseline characteristics will be summarized as continuous variables using descriptive statistics (n, mean, SD, median, minimum, and maximum) by study group (AV7909 Lot 1, AV7909 Lot 2, AV7909 Lot 3, AV7909 [three lots pooled], and BioThrax) and overall for ITT, Safety, and PP populations:

- Age (years)
- Baseline weight (kg)
- Baseline height (cm)
- Baseline BMI

The following demographics and baseline characteristics will be summarized as categorical variables with counts and percentages by study group and overall for ITT, Safety, and PP populations:

- Age (18 – 30, 31 – 50, and 51 – 65 years)
- Sex (Male, Female)
- Race (American Indian or Alaska Native, Asian, Black or African American, Native Hawaiian or Other Pacific Islander, White, More than one Race, and Other)
- Ethnicity (Hispanic or Latino, Not Hispanic or Latino, Unknown)

Subject demographics and baseline characteristics data listings will be provided.

5.3.2 Medical History

Medical history that occurred in 1% or more participants in either AV7909 or BioThrax group will be tabulated by system organ class (SOC) and preferred term (PT), according to the Medical Dictionary for Regulatory Activities (MedDRA) for Safety population. A listing of medical history will be provided.

5.4 Treatment Compliance

The IP will be administered to the subject by the unblinded investigational site staff in a controlled, clinical environment with the date and time of vaccinations recorded (refer to the exposure analysis in [Section 7.1](#)).

6 IMMUNOGENICITY ANALYSIS

All the immunogenicity tabulations and figures will be based on the PP population as defined in [Section 3.2](#). Immunogenicity outcome measures will be assessed by TNA NF₅₀. The validated LLOQ for TNA NF₅₀ is 0.064 ([BBRC Study 762-G004690](#)). TNA NF₅₀ values below the LLOQ will be imputed as 0.032 in the calculations of Mean/SD/GMT, which is half of the LLOQ of the assay. In the descriptive summary and data listing, TNA NF₅₀ values which are below the LLOQ will be presented as “< LLOQ”.

6.1 Summary of Immunogenicity Data

The summary of immunogenicity response TNA NF₅₀ by visit for each of three lots of AV7909 study groups, AV7909 group (three lots pooled), and BioThrax group will include:

- Descriptive summaries (n, median, minimum, and maximum) of TNA NF₅₀ values
- Geometric mean titer (GMT) and corresponding 95% CIs for TNA NF₅₀ calculated by taking the anti-logarithms of the mean and 95% CIs for log₁₀ TNA NF₅₀
- Proportion of participants with TNA NF₅₀ ≥ 0.56 (also TNA NF₅₀ ≥ 0.29 and TNA NF₅₀ ≥ 0.15) with associated 95% CI (exact Clopper Pearson confidence limit).

Line plots of GMT with associated 95% CI for TNA NF₅₀ by study group over time will be provided. Reverse cumulative distribution curve for TNA NF₅₀ values on Day 29 and Day 64 will be provided.

6.2 Primary Immunogenicity Endpoints

6.2.1 AV7909 Lot Consistency

6.2.1.1 Lot Consistency Based on GMT Ratio of TNA NF₅₀ at Day 64

The AV7909 lot consistency analysis is performed by pair-wise comparison of the two-sided 95% CI on GMT ratio for TNA NF₅₀ in each pair of lots (Lot 1 vs. Lot 2, Lot 2 vs. Lot 3, and Lot 1 vs. Lot 3) on Day 64. The lot consistency endpoint based on the GMT ratio for TNA NF₅₀ will be met if all three 95% CIs fall within the equivalence range of [0.5, 2.0]. The linear regression model will be fitted with log₁₀ NF₅₀ (Day 64) as the dependent variable and lot as the independent variable (categorical), assuming common residual variance. The mean differences in log₁₀ NF₅₀ between all pairs of lots will be calculated with 95% CIs. These will be transformed (anti-log) back to the scale of GMT ratios.

6.2.1.2 Lot Consistency Based on Protective Level of Immunogenicity at Day 64

The protective level of immunogenicity in each of the three AV7909 lots at Day 64, under the US FDA's Animal Rule, is assessed by the proportion of participants with TNA NF₅₀ values ≥ 0.56 on Day 64. The proportion and two-sided 95% CI (exact Clopper-Pearson confidence limits) for the proportion will be provided for each of the three AV7909 lots. This lot consistency based on the protective level of immunogenicity will be met if the LB of the two-sided 95% CI of the proportion is $\geq 40\%$ for all three AV7909 lots.

6.2.2 AV7909 Immunogenicity

6.2.2.1 AV7909 Immunogenicity at Day 64

The immunogenicity of AV7909 on Day 64 will be assessed by the proportion of participants pooled across all three AV7909 lots with TNA NF₅₀ values ≥ 0.56 on Day 64. The proportion and two-sided 95% CI (exact Clopper-Pearson confidence limits) for the proportion will be provided for the combined AV7909 group (three lots pooled). AV7909 will be considered as achieving a protective level of immunogenicity at Day 64 if the LB of the two-sided 95% CI of the proportion is $\geq 40\%$.

6.2.2.2 AV7909 Immunogenicity Based on Non-inferiority vs BioThrax at Day 64

Non-inferiority of AV7909 versus BioThrax on Day 64 is satisfied if the LB for the two-sided 95% lower CI of the difference (AV7909 - BioThrax) in the proportion of participants with TNA NF₅₀ values ≥ 0.29 in the combined AV7909 group (three lots pooled) versus BioThrax group is $> -15\%$.

The within-group proportions and the associated two-sided 95% CIs (exact Clopper-Pearson confidence limits) will be provided for the combined AV7909 group (three lots pooled) and

BioThrax group. The treatment difference in proportion between the combined AV7909 group and BioThrax group and two-sided 95% lower CI will be calculated using Newcombe score method.

6.3 Secondary Immunogenicity Endpoint

The immunogenicity of AV7909 on Day 29 will be assessed by the proportion of participants in the combined AV7909 group (three lots pooled) with TNA NF₅₀ values ≥ 0.15 on Day 29. The proportion and two-sided 95% CI (exact Clopper-Pearson confidence limits) for the proportion will be provided for the combined AV7909 group (three lots pooled), and the LB of the CI is compared with the success criterion of 67%. AV7909 will be considered as achieving a protective level of immunogenicity under the US FDA's Animal Rule at Day 29 if the LB of the two-sided 95% CI of the proportion is $\geq 67\%$.

